2.5 Food Preparation

Food Handler-Certified staff prepare all study food within a metabolic kitchen. Carbohydrateand protein-rich foods are weighed to the nearest 0.4 grams, while fat-rich foods are weighed to the nearest 0.2 grams. This permits fluctuations of <8 kilojoules (2 kcal) per food item. All food is ready-to-eat, except for the frozen fruit smoothies, which participants prepare at home using a high-speed Vitamix blender (Vita-mix Corporation; Olmstead Township, OH). Participants pick up the study food twice per week.

2.6 Weight Stability

Participants are kept weight stable by being fed enough to maintain their baseline body weight. At baseline, daily energy requirements for each participant are estimated using the National Institute of Diabetes and Digestive and Kidney diseases (NIDDK) Body Weight Planner (BWP)³, using an assumed activity factor of 1.5., and the results are rounded to the nearest 105 kilojoules (25 kcal). To ensure participants are weight stable, we weigh participants once a week, in tandem with their food pick-ups. Weight stability is defined as being within 2.3 kg (5 lbs) or 2% (if they weigh more than 113.4 kg [250 lbs]) of baseline body weight. Participants whose weight drifts toward the outer limits of the target range will have their energy intake adjusted, typically in 418-837 kJ (100-200 kcal) increments, to maintain weight stability.

2.7 Compliance

To ensure compliance during the controlled-feeding intervention, participants record themselves while preparing smoothies and eating all provided study food. We are using a previously validated method called remote video monitoring.⁴ In brief, we provide participants with an encrypted smartphone and tripod and teach them how to record themselves. Participants record themselves while eating all the provided food and preparing the smoothies. Research staff review the recorded videos for compliance and estimate the portion sizes of any uneaten food. We quantify compliance in based on the percent of the provided food calories consumed. Compliance rates below 80% or dishonesty are grounds for withdrawal.

3. Assessments

We will perform all assessments as detailed below.

3.1 Achieving Non-Diabetic Glycemia Without Antihyperglycemic Medications

One of the three objectives of this trial is to determine whether T2D remission may be possible without losing weight. After this trial was launched, an ADA-convened consensus group published new guidelines in August 2021 for defining diabetes remission,⁵ which conflicted with the original definition we had planned to use. Diabetes remission is now defined as achieving HbA1c <6.5%, or in some cases, a mean 24-hour mean glucose levels over a two-week period

(also called the Glucose Management Index [GMI]) <140 mg/dl, at least three months after ceasing all glucose-lowering medications. Given the new definition, we will assess whether participants can wean off all antihyperglycemic medications and achieve the same glycemic criteria, as a proxy for whether T2D remission may be attainable. (The only difference is that the new remission guidelines require a 3-month minimum period without antihyperglycemic medications.) In this clinical trial, non-diabetic glycemia will be defined as achieving mean 24hour glucose values of <140 mg/dl (equivalent to HbA1c<6.5%) over the past week.

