1.1 Objectives and Novelty

We will determine the effects of a whole-fruit-rich diet on glycemic control, liver fat, pancreatic fat, and cardiovascular disease risk factors in weight-stable adults with T2D. Our objectives are three-fold:

- Determine the effects of a diet rich in whole fruit on glycemic control in people with T2D;
- Determine whether T2D remission—or weaning off all diabetes medications and achieving non-diabetic glycemia—is possible without losing weight;
- 3. To determine how eating a diet high in fructose and simple sugars from whole-food sources affects liver fat.

Our clinical trial is novel for three reasons. We will conduct the first rigorously designed clinical trial to support (or refute) current American Diabetes Association (ADA) guidelines that patients with T2D should consume whole fruit. Second, to our knowledge, our study is the first interventional trial to test the effects of eating large doses of whole fruit as a food group. Third, our study is the first dietary trial to test whether patients with T2D can wean off all diabetes medications and achieve non-diabetic glucose levels *without losing any weight*. If this is true, it will be an important milestone achievement.

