1.3 Primary and Secondary Outcomes

The primary outcome is glycemic control. Glycemic control is difficult to accurately assess whenever antihyperglycemic medications doses change, as changing doses can mask improvements in standard glycemic outcomes. Therefore, we define an individual has having an improvement in glycemic control if s/he needs a lower dose of antihyperglycemic medications (if medication doses change) or has lower mean glucose levels (if medication doses do not change). We will use the following hierarchy of glycemic outcomes:

- 1. Achieving non-diabetic glycemia without antihyperglycemic medications (assessed as a binary outcome and analogous to T2D remission without the 3-month requirement);
- Total dosage of antihyperglycemic medications, as measured by the medication effect score (MES);
- 3. Mean glucose during a three-hour OGTT; and
- 4. Mean 24-hour glucose as measured by continuous glucose monitoring (CGM), adjusted for any changes in medication doses via the MES (see Section 4.5).

We decided to use mean 24-hour glucose as measured by CGM in lieu of HbA1c because CGM more accurately assesses the present glycemic status over the previous week, whereas HbA1c is a lagging indicator of glycemic control. The hierarchy implies that a positive or negative outcome in an upper level will always supersede any findings from lower levels in the hierarchy. In particular, if glucose-lowering medication dosages change, then assessments 1 and

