3.2 Cessation of Glucose-Lowering Medications

At the end of week 10, we will cease all antihyperglycemic medications in participants who achieve a mean 24-hour glucose of <140 mg/dl for at least one week during weeks 8–10. Participants whose baseline 24-hour glucose values are <140 mg/dl must additionally experience a 10% reduction in mean 24-hour glucose to ensure they have genuinely experienced a clinically meaningful improvement. Prior to week 10, participants' medications will not be adjusted unless there are safety concerns or associated adverse events.

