Appendix

Table S1. Eligibility Criteria.

Inclusion Criteria

- Aged 20–70 years
- BMI \leq 45.0 kg/m²
- First diagnosed with T2D within the past six years
- HbA1c between 6.0–9.5%

Exclusion Criteria

- On insulin
- Diagnosis of diabetes before age 18
- eGFR <45 ml/min per 1.732 m²
- Heart attack in the past six months or severe or unstable heart failure
- Significant gastrointestinal disease, major gastrointestinal surgery, or gallstones
- Significant cardiovascular, renal, cardiac, liver, lung, adrenal, or nervous system disease that might compromise the participant's safety or data validity
- Evidence of cancer (other than non-melanoma skin cancer) within the last five years
- Clinically significant laboratory abnormality
- Change in the dosage of a chronic medication that may affect study endpoints within the past three months
- On weight loss medication
- Lost or gained >5 kg of weight in the past six months
- Pregnant, planning to become pregnant in the next 12 months, or breastfeeding
- Major psychiatric condition that would affect the ability to participate in the study
- Not able to eat the provided study meals (e.g., food allergies)
- Behavioral factors or circumstances that may impede adhering to the dietary intervention
- Not able to do the abdominal MRI scan (e.g., claustrophobia, implanted metal objects, body diameter >60 cm)
- Not willing to wear a mask and/or comply with other COVID-19 precautions

Figure S1. Study Menu. Shown below is the 7-day menu during the main phase of the study

(weeks 5-12).

Sunday	Monday	Tuesday	Wednesday	Thursday	Friday	Saturday						
Breakfast												
Mixed Berry	Raspberry	Peach Smoothie	Strawberry	Cherry	Mango	Blueberry						
Smoothie	Smoothie	reach Shioothic	Smoothie	Smoothie	Smoothie	Smoothie						
Lunch												
Tomato-Garlic	Corn,	Farro and	Chickpeas and	Sweet Potato	Oatmeal	Vegetable and						
Lentil Bowl	,,, _,, _		Broccoli with	and Kidney		Hummus						
	Sweet Pepper	Vegetables with	Pesto Parmesan	Bean Bowl	Soy Milk	Sandwich on						
Walnuts	ts Salad Mozzar					Ezekiel Bread						
			Dried Figs	Pumpkin Seeds	Pecans							
Dried Mango	Brazil Nuts	Almonds			_							
	D 1 1 D 1			Dried	Dates	Almonds						
	Dried Peaches	Dried Apricots		Pineapple		D' 1E'						
						Dried Figs						
	1	2	Snack (Fruit Sala	d)	I	1						
Clementines,	Strawberries,	Blueberries,	Cantaloupe,	Clementines,	Strawberries,	Cantaloupe,						

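### Level 1 counts any drug-free completer with non-diabetic glycemia, so never-treated participants could make it significant with nobody weaned; only completers treated at baseline can support the weaning claim

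*Combined protocol and SAP*

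**What the plan says.** Three places describe a transition from treated to untreated. Section 1.1 (Objectives and Novelty) sets the objective as "weaning off all diabetes medications and achieving non-diabetic glycemia" and presents the trial as the first dietary test of whether "patients with T2D can wean off all diabetes medications and achieve non-diabetic glucose levels" with no weight loss. Section 1.2 hypothesises the same for some participants. Section 3.1 says "we will assess whether participants can wean off all antihyperglycemic medications and achieve the same glycemic criteria", as a proxy for remission.

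The outcome that is tested is a state. The first level of the primary hierarchy in Section 1.3 is "Achieving non-diabetic glycemia without antihyperglycemic medications (assessed as a binary outcome". Section 3.1 then defines the glycemic part as mean 24-hour glucose under 140 mg/dl ("equivalent to HbA1c<6.5%) over the past week"). Section 4.4 compares one observed rate, in completers, with a spontaneous remission rate by an exact binomial test. It does not restrict or stratify by baseline treatment.

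On who can enter, the inclusion criteria in Table S1 cover age, BMI, time since diagnosis and "HbA1c between 6.0–9.5"%. Insulin users are excluded, but current use of a glucose-lowering drug is not required.

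One safeguard appears in Section 3.2: "Participants whose baseline 24-hour glucose values are <140 mg/dl must additionally experience a 10% reduction in mean 24-hour glucose". It is written as a condition for stopping drugs at week 10, not as part of the Level 1 definition.

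**The concern.** A completer who takes no glucose-lowering drug at baseline and moves from, say, 160 to 135 mg/dl is a Level 1 event under Section 1.3. That completer says nothing about weaning, because there was no drug to stop. The 10% condition does not reach this person either, since it is attached to stopping drugs. An untreated participant already below 140 mg/dl at entry could even count without any fall. Entry from HbA1c 6.0% allows this, as Section 3.1 equates 140 mg/dl with 6.5%.

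Level 1 heads a hierarchy in which upper levels override lower ones, and Section 1.1 calls a positive answer on weaning an important milestone. A significant Level 1 result could therefore be read as evidence that patients weaned off their drugs when none did. The plan does not say how untreated completers are classified, or which denominator the weaning statement uses.

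**Working it through.** **Inputs.** 16 completers, 18.0% alternative, 0.7% null and 81% power (Section 4.3); 0.07% null and exact binomial test (Section 4.4, Statistical Analyses); two-sided α=0.05 (Section 4.4). The number untreated at baseline is not given, so every value for it below is assumed.

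**1. Reproduce the plan's power.** With n=16 and null 0.007:
- One event: P(X≥1) = 1 − 0.993^16 = 0.106, not significant.
- Two events: P(X≥2) = 1 − 0.993^16 − 16 × 0.007 × 0.993^15 = 0.0055, significant. The two-sided exact p-value is the same.
- Power at 18%: 1 − 0.82^16 − 16 × 0.18 × 0.82^15 = 0.811. This matches the stated 81%.

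**2. Events needed under the null printed in Section 4.4.** With null 0.0007, one event gives 1 − 0.9993^16 = 0.011. One completer is then enough, and power at 18% is 1 − 0.82^16 = 0.958.

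Nothing in the definition prevents those one or two events from all being never-treated completers.

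**3. How often this could happen (assumed values).** Let k of 16 be untreated, each with probability 0.30 of being below 140 mg/dl at week 12. Let treated completers wean at exactly the null rate p0. With X ~ Bin(k, 0.30) and Y ~ Bin(16 − k, p0), Level 1 is significant when X + Y reaches the required count.

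| Untreated (assumed) | Null 0.7%, two events needed | Null 0.07%, one event needed |
|---|---|---|
| 0 | 0.0055 | 0.011 |
| 2 | 0.131 | 0.515 |
| 4 | 0.382 | 0.762 |

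For k=4 at 0.7%: P(X+Y≤1) = 0.2401 × (0.9192 + 0.0778) + 0.4116 × 0.9192 = 0.618, and 1 − 0.618 = 0.382. If the 0.30 is changed to 0.20 or 0.50, the k=4 figures become 0.215 or 0.708 at 0.7%, and 0.594 or 0.938 at 0.07%.

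**4. Power for the weaning rate alone.** The denominator is completers treated at baseline, with the true rate held at the plan's 18%. At 0.7%, two events are needed for each n shown, and power is 1 − 0.82^n − n × 0.18 × 0.82^(n−1). At 0.07%, one event is needed, and power is 1 − 0.82^n.

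| Treated (assumed) | Power at 0.7% | Power at 0.07% |
|---|---|---|
| 16 | 81.1% | 95.8% |
| 14 | 74.7% | 93.8% |
| 12 | 66.4% | 90.8% |
| 10 | 56.1% | 86.3% |

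**The case against.** **The tested endpoint is one thing throughout.** The Section 1.3 outcome, the heading of Section 3.1, the power statement and the Section 4.4 test all describe a drug-free state. The weaning sentence in Section 3.1 gives the purpose, not the event definition. This stands. A reader might infer that the plan holds two rival endpoint definitions, or that Level 1 is invalid. The documents do not support that: the mismatch is between a consistent endpoint and the claim to be drawn from it.

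**Section 1.3 partly deals with it.** It sends cases without a change in glucose-lowering drugs to the OGTT and CGM assessments. Read participant by participant, that would take a never-treated completer out of Level 1. But Section 4.4 does not carry the rule into the binomial test, so the gap is narrowed and not closed.

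**Untreated completers do not escape a drug-free test.** They are off drugs for all 12 weeks, against about two weeks for someone stopped at the end of week 10. This also stands. Their result is a fair test of drug-free glycemia; it is simply uninformative about weaning.

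**The 81% is not wrong.** It is correct for the endpoint Section 4.3 names, and that section says the sample size did not rest on a power calculation. A reader might infer that power really falls to 56%. That figure needs the 0.7% null, only 10 treated completers and an unchanged 18% rate; under 0.07%, power stays at 86% or more for 10 to 16 treated.

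**There may be no untreated participants, and with 16 people each case's drug history can be looked up.** Both are true. Looking it up afterwards still does not fix the numerator and denominator in advance. Section 5 records that some team members had seen medication data from the first three completers when the analysis plan was revised.

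**Conclusion.** The point holds as a mismatch between what Level 1 tests and what Section 1.1 wants to conclude. As written, Level 1 can be significant with nobody weaned: two never-treated events suffice against 0.7% (p=0.0055), and one against 0.07% (p=0.011). This is what the definition permits, not a forecast. The documents do not show that any untreated participant is enrolled, and if all 16 completers are treated at baseline the problem disappears. The probabilities of a misleading positive result and the reduced power figures rest on assumed untreated numbers, and the first also on an assumed response rate. The conflict between 0.7% and 0.07% is a separate matter, but it decides how many events suffice and whether restricting the denominator costs much power. The stated 81% reproduces only with the two-event rule that 0.7% implies.

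**What to change.** In Sections 1.3 and 4.4:

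1. Reconcile the 0.7% and 0.07% null rates first.
2. Keep the pooled rate as the Level 1 result, labelled as non-diabetic glycemia without drugs, and say whether the 10% condition in Section 3.2 is part of that outcome definition.
3. Report the pooled rate split by baseline drug use. Let only the rate among completers taking one or more antihyperglycemic drugs at baseline, in both numerator and denominator, support the Section 1.1 weaning claim. Report never-treated completers separately.
4. In Section 4.3, state that 81% applies to the pooled endpoint with n=16 and the 0.7% null, and to the weaning rate only if all 16 are treated at baseline. Under 0.7% and the same 18% rate, give 75%, 66% and 56% for an assumed 14, 12 and 10 treated.

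This is a change of wording and reporting. Table S2 already records medication at week 0, so no new data are needed. The cost is a smaller denominator, and so less precision, for the weaning claim.

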2 will supersede assessments 3 and 4 since changes in glucose-lowering medications confound the interpretation of glycemic data. If there are no changes in glucose-lowering medications, then we will use assessments 3 and 4 to determine whether there are changes in glycemic control. We will interpret the data from assessments 3 and 4 as follows. We will interpret assessment 3 (OGTT) to indicate whether the intervention improves or exacerbates glucose intolerance and underlying defects in glucose metabolism. If there is no change in assessments 1-3, we will interpret assessment 4 (CGM) to reflect only acute changes in the glycemic load and macronutrient composition of the diet. For instance, the intervention may increase mean 24-hour glucose levels in a participant who eats a low-carbohydrate diet at baseline, but this increase may simply reflect switching to a higher carbohydrate diet, not a worsening of glucose metabolism.¹ As another example, the intervention may decrease mean 24-hour glucose levels in a participant who eats a higher glycemic load diet at baseline, but this decrease may reflect switching to a lower glycemic load diet, not an improvement in glucose metabolism per se.

The secondary outcomes are liver fat, pancreatic fat, cardiovascular risk factors, and ancillary measures of glucose metabolism:

- Liver fat, as measured by magnetic resonance imaging and spectroscopy (MRI/S);
- Pancreatic fat, as measured by MRI/S;
- Insulin secretion, as measured by the oral minimal model;
- Insulin sensitivity, as measured by the oral minimal model;
- Mean insulin and C-peptide levels during the OGTT;
- Time-in-range metrics from CGM;
- Mean amplitude of glycemic excursions from CGM;
- HbA1c;

- Fasting glucose;
- Blood pressure;
- Heart rate; and
- Lipids (total cholesterol, LDL cholesterol, HDL cholesterol, and triglycerides).

Additional outcomes include body composition (subcutaneous abdominal fat, visceral fat, and waist circumference), preferences for and sensitivity to sweet tastes, diet satisfaction, food cravings, eating behaviors, mood, quality of life, and depression.

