4.4 Statistical Analyses

All statistical tests will be two-sided with a Type I error rate of α =0.05. Because this is a controlled-feeding trial—designed to determine the cardiometabolic effects under conditions of nearly perfect adherence—we will analyze the data per protocol in completers only. The primary comparison will be between weeks 0 and 12, with secondary comparisons between weeks 0 and 4 and between weeks 4 and 12. Data may be Winsorized if there are outliers with an overwhelming degree of influence or values that are non-physiologic . We will test whether a fruit-rich diet can induce non-diabetic glycemia without hyperglycemia medications by testing whether our observed "remission" rate differs from the spontaneous T2D remission rate of

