0.07% using an exact binomial test.²³ If there is one or more cases of non-diabetic glycemia, then the true rate is non-zero, and we will report a 95% confidence interval derived from bootstrapping. All other data will be analyzed as change scores. For all continuous data and Likert score data with at least four levels and sufficient variability, we will use linear mixed models with time as either a linear or categorical effect and with a random intercept for participants. For other data types, we will use distribution-appropriate generalized linear mixed models. Alternatively, if spline models are more parsimonious than treating time as a linear or categorical effect, we will use generalized-additive models with penalized adaptive regression splines instead. To analyze the data from CGM, we will perform a trajectory analysis to determine whether there are different "response phenotypes." Since it is conceivable that participants starting from very different baseline diets may have distinct trajectories early on, we may also consider a trajectory analysis of the data with special attention to the Ramp-Up phase and restrict the models to the Main Phase period after the trajectories converge. We will consider adjusting for covariates such as baseline values or mean 24-hour glucose levels only if statistically and clinically merited. For the inferential statistics on continuous variables, we will test for differences using least squares means evaluated at study timepoints, or alternatively, if time is most appropriately treated as a categorical variable, by the significance of the coefficient for each timepoint. We will analyze change in categorical variables using McNemar's test for dichotomous variables and Bowker's test of symmetry for variables with more categories. Finally, to assess inter-individual responses in the vein of precision nutrition, we will also report the percentages of participants who experience an improvement, no change, and a worsening in glycemic control.

5. Protocol Amendments

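### An untreated participant whose baseline mean 24-hour glucose is already below 140 mg/dl can count as a level-1 remission without any change, because the binomial test does not say who is at risk

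*Combined protocol and SAP*

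**What the plan says.** Section 1.3 puts a binary outcome at the top of the primary hierarchy: non-diabetic glycemia without antihyperglycemic drugs. A result at this level overrides the levels below it. Section 3.1 gives the criterion: "non-diabetic glycemia will be defined as achieving mean 24hour glucose values of <140 mg/dl (equivalent to HbA1c<6.5%) over the past week".

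Eligibility (Section 1.5 and Table S1) asks for "HbA1c between 6.0–9.5" percent. It excludes insulin, weight-loss drugs and recent dose changes, but does not require any antihyperglycemic drug.

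Section 3.2 anticipates low baselines: "Participants whose baseline 24-hour glucose values are <140 mg/dl must additionally experience a 10% reduction in mean 24-hour glucose". This sentence belongs to the week-10 rule for stopping drugs.

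Section 4.4 analyses completers and asks by an exact binomial test whether the observed "rate differs from the spontaneous T2D remission rate of" 0.07%, with a bootstrap confidence interval if there is at least one case. It then says "All other data will be analyzed as change scores". Section 4.3 gives the spontaneous rate as 0.7% and states 81% power for a true rate of 18.0% with 16 completers.

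**The concern.** A participant on a drug cannot be in the level-1 state at week 0. An untreated participant at or above 140 mg/dl has to fall to reach it. An untreated participant below 140 mg/dl is in it from the start, and the extra reduction in Section 3.2 does not reach someone who has no drug to stop.

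A comparison with a spontaneous remission rate makes sense only among people who could still enter remission. Level 1 is the one outcome that Section 4.4 does not analyse as change, and its denominator is all completers. An unchanged participant of this kind would add a success that owes nothing to the diet. Rejection needs only one or two successes, so very few such participants could decide the highest-ranked primary result.

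**Working it through.** **Can the case arise?** Section 3.1 equates HbA1c 6.5% with 140 mg/dl. Section 3.5 uses 28.7 mg/dl per unit of the medication effect score, and by Section 3.3 that unit is one HbA1c percentage point. At the lower entry limit: 140 − 0.5 × 28.7 = 125.65 mg/dl. On average, an HbA1c from 6.0% to just under 6.5% therefore corresponds to about 126–140 mg/dl, which already meets the criterion. An individual's CGM mean can differ from this.

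**Reproducing the plan's power.** Inputs: n = 16, two-sided α = 0.05, null 0.7%, alternative 18.0%.
- One success: p = 1 − 0.993^16 = 0.106. Two successes: p = 0.0055. Rejection needs 2 of 16.
- Power = 1 − 0.82^16 − 16 × 0.18 × 0.82^15 = 1 − 0.0418 − 0.1468 = 81.1%, against the stated 81%.
- At 0.07%, one success gives p = 1 − 0.9993^16 = 0.011, so 1 of 16 is enough. Power is 1 − 0.82^16 = 95.8%.

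**False rejection with no diet effect.** Two quantities are assumptions, since the documents give neither: k, the number of untreated completers with baseline below 140 mg/dl, and q, the probability that each is below 140 mg/dl at week 12 anyway. The other 16 − k completers succeed at the null rate. The error is P[Bin(k, q) + Bin(16 − k, null) ≥ cutoff].

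Null 0.7%, cutoff 2:
- k = 1: q × P(X₁₅ ≥ 1) + (1 − q) × P(X₁₅ ≥ 2) = q × 0.1000 + (1 − q) × 0.0048. This is 0.0524 at q = 0.5 and 0.1000 at q = 1.
- k = 2: q² + 2q(1 − q) × P(X₁₄ ≥ 1) + (1 − q)² × P(X₁₄ ≥ 2). With P(X₁₄ ≥ 1) = 1 − 0.993^14 = 0.0937 and P(X₁₄ ≥ 2) = 0.0042, q = 0.5 gives 0.25 + 0.0468 + 0.0011 = 0.2979.

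Null 0.07%, cutoff 1:
- k = 1: q + (1 − q) × 0.0104, which is 0.5052 at q = 0.5 and 1 at q = 1.

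| k | null 0.7%, q = 0.5 | null 0.7%, q = 1 | null 0.07%, q = 0.5 | null 0.07%, q = 1 |
|---|---|---|---|---|
| 0 | 0.55% | 0.55% | 1.1% | 1.1% |
| 1 | 5.2% | 10.0% | 50.5% | 100% |
| 2 | 29.8% | 100% | 75.2% | 100% |

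Each such success also adds 1/16 = 6.25 percentage points to the reported rate.

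**With those participants left out.** The cutoffs do not change. False rejection is 0.48% (n = 15) or 0.42% (n = 14) at the 0.7% null, and about 1.0% at either size at the 0.07% null.

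**The case against.** The strongest reply is that the plan shows a different intent. Sections 1.1 and 3.1 speak of weaning off drugs, which an untreated person cannot do. Section 1.3 counts someone as improved without a dose change only if that person "has lower mean glucose levels (if medication doses do not change", and adds "If there are no changes in glucose-lowering medications, then we will use assessments 3 and 4". Section 4.4 also reports the percentages improved, unchanged and worsened, where an unchanged participant would show as unchanged. All of this stands, and it rules out one tempting inference, that the plan means to count unchanged people as remissions. But these are rules of interpretation. None says whether such a participant is a success, a failure or outside the denominator of the binomial test. McNemar's test, also in Section 4.4, would ignore unchanged pairs, but level 1 is assigned to the binomial test.

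Second, the size rests on assumptions. No passage says that an untreated participant with a low baseline is enrolled. The 100% entries follow by construction, because guaranteed successes reach the cutoff. With k = 1 at the 0.7% null, the error stays below 5% for q under about 0.47: it is 4.3% at q = 0.4 and 2.4% at q = 0.2. Section 1.3 itself notes that the diet may raise 24-hour glucose after a low-carbohydrate baseline, so q need not be near 1. This stands too. At the 0.07% null, though, the error passes 5% once q exceeds (0.05 − 0.0104)/(1 − 0.0104) = 0.04.

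Third, the 10% reduction in Section 3.2 could be written into the outcome for untreated participants, which would keep all 16. That is a possible clarification. It would, however, compare a further fall in people who already meet the criterion with a rate of entering remission, and these are different events.

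**Conclusion.** The gap is real. As written, an untreated completer who starts and stays below 140 mg/dl meets the level-1 definition and enters the binomial test as a success. For q between 0.5 and 1, one such participant raises false rejection to 5.2–10.0% at the 0.7% null or 50.5–100% at the 0.07% null. Two raise it to 29.8–100% at the 0.7% null. Every figure depends on assumed k and q and on which null applies.

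A reader might infer that the trial's remission result will be false, or that its type I error is known to be inflated. The documents support neither. They do not give the number of such participants, and with none the test behaves as planned. The conclusion is that a false positive is possible under the written rule and that the rule should be closed before the analysis.

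**What to change.** State in Section 4.4 that the level-1 binomial test, its denominator and its confidence interval cover only completers who do not already meet level 1 at week 0: those on at least one antihyperglycemic drug, or with baseline mean 24-hour glucose of 140 mg/dl or more. Report the others through assessments 3 and 4. Give the all-completers rate as descriptive only, with baseline drug and glucose status beside each success. Date and disclose the change, because Section 5 records that team members had seen medication and HbA1c data from the first three completers.

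The change is to wording only, since Table S2 already schedules week-0 CGM and medication data, and it leaves the drug-stopping rule untouched. The cost is a possibly smaller denominator and less power for an 18% rate:

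| n | power, null 0.7% | power, null 0.07% |
|---|---|---|
| 16 | 81.1% | 95.8% |
| 15 | 78.1% | 94.9% |
| 14 | 74.7% | 93.8% |

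An untreated participant just above 140 mg/dl at baseline stays in the test, so regression to the mean near the threshold remains; listing baseline values makes it visible.

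Two separate matters should be settled alongside: the conflict between 0.7% (Section 4.3) and 0.07% (Section 4.4), and the rule in Section 3.12 for valid baseline CGM days in the first three completers, which is needed to classify them.
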